3.2.3 Mediators

Cognitive and Behavioral Mediators (Cronbach's alphas based on pilot sample N=84)

Oral health knowledge: Oral health knowledge is a 7-item true/false test based on previously developed knowledge test used with low income older African Americans (Slaughter & Evans, 2007) (Alpha=.66).

Oral health beliefs/norms: The Dental Coping Beliefs Scale (Wolfe, Stewart, Maeder, Hartz, 1996; Wolfe, Stewart, Hartz, 1991; Wardh & Sorensen, 2005) is a 26-item scale consisting of four subscales, Oral Health Beliefs, Internal Locus of Control, External Locus of Control, and Self-Efficacy. The scales were adapted in the pilot study and used to measure oral health beliefs, locus of control, and self-efficacy, key domains in the study model (Alpha = .61).

Oral Health Norms: We will measure social norms with a scale that measures the perceived importance of oral hygiene behavior (Alpha = .68 with 1 item deleted).

Oral Health Social Support: These are two questions asking how building residents participants can obtain oral health information; and from how many others who regularly work in or visit the building participants can obtain oral health information (Likert scale: none,1-2, 3-4, 5 or more).

Perceived Oral Health Risks: This is a five-item scale that assesses perceived risk of oral heal problems, including getting cavities, toothaches, gum problems, oral cancer and oral health problems that would cause a visit to the hospital. Participants rate the likelihood of having these problems on a four-point Likert scale, 1 (very unlikely) to 4 (very likely). Chronbach Alpha = 0.83.

Oral hygiene behaviors: A measure consisting of questions that assess oral health self-management behavior including frequency and timing of brushing, flossing teeth, cleaning dentures (3 items, Alpha = .71).

Oral health self-management fears and worries: A scale was developed from formative data collected through our prior studies and evaluated during the pilot consisting of items identified by residents in focus group sessions related to worries and fears about conducting oral hygiene behaviors. Dental Worries Scale (23 items) Alpha=.90; Dental Fears (4 items) Alpha = .75.

Oral Health Self-Management Intentionality: Intention to perform the oral health self-management behaviors, a critical component of the IM model, will be assessed using the protocol described by Ajzen and Fishbein (1980) and Tedesco, et al. (1991) and adapted based on formative data. Participants will be asked to rate their intention to brush and floss daily using a five item four point Likert scale Alpha=.81.3.2.4 Intervention Variables

Exposure to norms based campaign: *Dosage* will be assessed by: (a) reported attendance at each campaign activity (three), and (b) number of activities respondent participated in at each event (passport).

Number of focal points addressed in intervention: This is a count based on respondents' score below the cutoff points for main cognitive and behavioral domains measured and addressed in the intervention.

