Our successful pilot intervention Changing Oral Health Norms and Hygiene Practices among Vulnerable Older Adults supported by NIDCR #R34 DE022271 (2011-2013) was based on Fishbein's modified theory of reasoned action called Integrated Model (IM) of Behavioral Prediction (Fishbein, 2008) operationalized through Adapted Motivational Interviewing (AMI) and Bandura's notions of self-efficacy and skills reinforcement operationalized through Practice-to-Mastery or PM (Liska, 1984; Connor, 2010). The pilot study was conducted in a single building of approximately 200 apartments in the Greater Hartford Area. It included two components offered sequentially, a face to face intervention (the AMI) with practice of oral hygiene skills to mastery (PM), and two campaign fairs promoted by a small committee of building residents. Post intervention, participants (n=30) demonstrated a significant improvement in the Plague Scores from a mean score at baseline of 84% (sd=11.8%) to 58% (sd=31.2%) at follow-up (p<0.001) and the Gingival Index from a mean baseline score of 1.2 (sd=0.56) to a mean follow-up score of 0.54 (sd=0.47), p<0.001. Differences in P-M skills scores from pre to post instruction in brushing and flossing, part of the AMI-PM session showed significant improvement. Brushing scores increased from 1.9 (fair/poor) prior to the AMI-PM session to 2.9 (good/excellent; p<0.001) after and flossing skills improved from 1.7 to 2.7 (p<0.001). In the intervention group, we found significant mean decreases (improvements) from pre to post in several important cognitive domains including perceived risk of oral disease which decreased from a mean of 2.5 to 2.0 (sd=.70 for both, p=.04) self-management worries which decreased from a mean of 1.36 (sd=.66) to 0.57 (sd=.97); p=.002) and self-management fears which decreased from a mean of 2.2 (sd=.81) to 1.53 (sd=.97; p=.001). In contrast, non-AMI respondents showed mean increases (deterioration) from pre to post in all three domains.

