Individuals who score below the cutoff point on each of the following domains in the survey (see appendix B) will require cognitive / behavioral intervention.

All AMIs will be recorded for process documentation purposes.

Dor	nain	Items	Cut-off points
1a.	ADLs	Need help with grooming, dressing, eating, brushing teeth/cleaning dentures.	Need help on any of these
	Oral health knowledg e	7-item knowledge test	<5 correct
3a.	Oral health self- efficacy	If you brush and floss correctly, you expect fewer dental problems; You believe that you know how mouth sores can be treated; If someone showed you how to clean your teeth, you would be able to practice better oral health care; If you knew the facts about dental disease, you would be able to practice better oral care; You believe you can remove most of plaque to help prevent cavities and gum disease;	Mean of items <3 (disagree and strongly disagree)
3b.	Locus of control	You believe tooth loss is a normal part of growing old	If response to this item was agree or strongly agree)
4a.	Oral Health Norms - Beliefs about Importance of oral hygiene	How important do you think the following behaviors are: Visit the dentist once a year; Brush your teeth at least once a day; Brush with fluoride toothpaste; Floss or clean between teeth at least once a day; Check for sores in the mouth	1 or 2 on any item (Not at all important; not very important)
	Oral health Social Support	Local access to health/oral health information	If all sources are "0" (none)
ба.	Oral hygiene behaviors	How often do you: Brush in a day	<2 times per day
7a.	Perceive d Oral Health Risks	What are the chances that you will Get cavities? Get a toothache? Have problems with your gums? Develop oral cancer? Have to go to the hospital for problems related to your teeth, gums or mouth?	Mean <3 (4 - very unlikely; 3 - unlikely; 2 - likely; 1 - very likely)

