8a.	Self- manage ment worries	How worried are you that: You cannot clean your dentures properly; You can't control your bad breath Medications you are taking may be affecting your teeth If you brush your teeth your gums might get irritated You don't brush your teeth enough When you floss there is bleeding You don't brush your teeth properly You are not using the correct toothbrush You don't know how to clean your tongue You don't know the best time to go to the dentist If you use mouthwash it might dry out your mouth Your mouth feels dry all the time If you take your dentures out you could lose them You might have to get dentures of false teeth made from dead men's teeth so you keep your bad teeth If you go to the dentist you might get a mouth or tooth infection or cancer You can't clean the teeth in the back of your mouth Your teeth may keep you from socializing Your bad teeth are keeping you from eating foods Your teeth get discolored When you try to brush you feel pain When you put your dentures in it hurts	Mean <3 for scale (4 = not at all; 3= not much)

9a. Self- manage ment fears	You are afraid: That bleeding gums may be a serious problem; You cannot clean your dentures properly; Of losing your teeth; Of oral cancer: That problems with your teeth and gums might affect your general health	Mean < 3 (4= not at all; 3 = not much)
10a. Oral Health Self- Manage ment Intention ality	What is the possibility that: You will brush your teeth at least twice a day? You will floss your teeth or clean between your teeth at least once a day? You will clean your mouth daily? You will check your mouth for loose teeth? You will visit the dentist in the next year for a check-up and screening for oral cancer?	Mean <1 (0= no possibility; 1= slight possibility)
11a. Dry mouth	Do you sip liquids to aid in swallowing dry foods?	Yes
12a. Diet	How often do you: Eat sweet snacks; Eat starchy snacks; Suck on hard candies; Drink/eat sweets after brushing at night; Drink fruit juice on an average day.	>2-3 times a day on any item.
Clinical Assessment	Plaque Score and Gingival Index	All participants

Practice to Mastery.

The following criteria are defined for practice to mastery scores during the intervention. AMI (and for mastery scores during T0, T1, T2 and T3 observation points*)¹

Excellent (4): (P-M) Is able to easily use the appropriate oral hygiene aids and correctly mimic the instruction from the video/live demonstration without additional instruction.

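### The perceived-risk scale carries opposite response keys in section 3.2.3 and in row 7a of the section 6 cut-off table, so the mean-below-3 trigger reverses direction if scores are not recoded

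*Combined protocol and SAP*

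**What the plan says.** Section 3.2.3 (Mediators) introduces the measure with "This is a five-item scale that assesses perceived risk" and says that participants rate likelihood "on a four-point Likert scale, 1 (very unlikely) to 4 (very likely"). On this key a high score means high perceived risk.

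The cut-off table in section 6 (Study Intervention), row 7a, lists the same five items (cavities, toothache, gum problems, oral cancer, hospital visit). It sets the rule "Mean <3 (4 - very unlikely; 3 - unlikely; 2 - likely; 1 - very likely"). On this key a high score means low perceived risk.

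The rule has consequences. Section 6 says of "Individuals who score below the cutoff point on each of the following domains in the survey" that they need intervention on that domain, and the first step of the session is to mark those domains on the Focal Point form. The intervention-variables text that follows the mediators in section 3.2.3 builds the focal-point count from whether respondents "score below the cutoff points for main cognitive and behavioral domains". Sections 12.1 and 12.4 define the Hypothesis 5 dosage through the talking points covered for the focal points addressed.

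Section 2.1 reports the pilot result, "perceived risk of oral disease which decreased from a mean of 2.5 to 2.0 (sd=.70 for both, p=.04"), and treats the fall as an improvement.

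**The concern.** A cut-off has a meaning only together with the key of the score it is applied to. Here the two keys are exact reversals, and both appear in current text with their labels. Under one, a mean below 3 picks out people who tend to think problems are likely. Under the other, it picks out people who tend to think them unlikely. The protocol does not say that scores are reversed between the survey and the cut-off.

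At stake is whether the perceived-risk script reaches the people the rule is meant to reach, and whether the focal-point count and the dosage measure built on it mean what the plan says. The pilot text does not settle the matter. A fall described as an improvement fits the 3.2.3 direction if lower perceived risk is the goal, whereas on the row 7a key the same fall would mean higher perceived risk.

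**Working it through.** The plan gives no figure of its own to reproduce here. The check is whether the keys conflict, who is affected, and how many that might be.

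**Inputs.** Five items scored 1 to 4 (3.2.3); the 3.2.3 key; the row 7a key and its trigger of mean below 3 (section 6); pilot baseline mean 2.5 and SD 0.70 (section 2.1).

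**Step 1, relation between the keys.** If x is a score on the 3.2.3 key, the row 7a score is 5 − x. The row 7a rule, 5 − x < 3, is therefore x > 2 on the 3.2.3 key. Applying the trigger to unreversed 3.2.3 scores gives x < 3 instead.

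**Step 2, uniform responders.**

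| Every item answered | Row 7a mean | Flagged on row 7a key | 3.2.3 mean | Flagged if unreversed |
|---|---|---|---|---|
| very unlikely | 4 | no | 1 | yes |
| unlikely | 3 | no | 2 | yes |
| likely | 2 | yes | 3 | no |
| very likely | 1 | yes | 4 | no |

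All four change status.

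**Step 3, everyone else.** The rules x > 2 and x < 3 agree only when 2 < x < 3, and both then flag the person. Anyone with x ≤ 2 or x ≥ 3 changes status. Of the 4^5 = 1024 possible answer patterns, 802 are flagged under each key: 580 under both, 222 under row 7a only, 222 under the unreversed key only, and none under neither. So 222 + 222 = 444 patterns change status. This counts patterns, not people.

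**Step 4, illustrative size in people.** Take x as normal with mean 2.5 and SD 0.70.

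- Unreversed: P(x < 3) = Φ((3 − 2.5)/0.70) = Φ(0.714) = 0.762.
- Row 7a key: P(x > 2) = 1 − Φ((2 − 2.5)/0.70) = 0.762.
- Both: 0.762 − (1 − 0.762) = 0.525, from unrounded values.
- Change of status: 1 − 0.525 = 0.475, about 48%.

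Five-item means move in steps of 0.2. With a continuity correction (boundaries 2.9 and 2.1), each key flags 0.716, both flag 0.432, and 1 − 0.432 = 0.568 change status. The range is about 48% to 57%. Because 5 − 2.5 = 2.5, these baseline figures are the same whichever key the pilot used.

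**Step 5, where the score goes.** Perceived risk is described as a mediator in 3.2.3. It is absent from the targeted mediators in the section 6 conceptual framework, and from the section 12.4 lists for the causal-pathway, Hypothesis 3 and latent-change analyses.

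**The case against.** The strongest reply is that row 7a prints its key beside the cut-off, in the same orientation as the worries and fears rows, so staff using the table can apply the rule as written. An error then needs survey data that are coded as in 3.2.3 and not recoded. The documents do not show that this happens, and the survey and Focal Points Checklist sit in an external appendix. This stands: the consequence is conditional, although the conflict in the text is not.

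It is also fair that perceived risk is one of twelve numbered domains. Interventionists may add areas from the discussion, and dosage is a proportion, so one domain more or fewer changes numerator and denominator together. That limits the damage but does not say who should be flagged.

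Four stronger readings are tempting and should not be drawn.

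- **That the two keys select opposite people.** They do not: anyone with a mean strictly between 2 and 3 is flagged under both.
- **That the mediation results change sign.** The section 12.4 models do not list perceived risk. Even for a modelled mediator, reversal changes the sign of both component paths, and the indirect effect is unchanged: (−a)(−b) = ab.
- **That the worries and fears scales show the same contradiction.** Section 3.2.3 gives no response key for either. The contrast is with pilot scores, where falls (worries 1.36 to 0.57, fears 2.2 to 1.53) count as improvement, while rows 8a ("Mean <3 for scale (4 = not at all; 3= not much")) and 9a make higher scores favourable. A mean of 0.57 is impossible if the lowest code is 1, so the pilot may have been coded differently. That warrants a check only.
- **That the gap widens to 92% against 50% flagged, from the pilot follow-up mean of 2.0.** That mean follows both pilot components. In this trial tailoring uses T0, or T1 after the campaign alone, so no cut-off is applied in that state.

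**Conclusion.** The point holds in a limited form. Section 3.2.3 and row 7a give mirror-image keys for the same five items, and the visible text states no reversal. If 3.2.3 scores are used unreversed, the trigger changes direction, and everyone with a mean of 2 or below, or of 3 or above, is classified differently. That result needs no distributional assumption.

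The figure of about 48% (up to 57% with the continuity correction) is an illustration. It assumes that the baseline mean and SD of a small single-building pilot apply here and that scores are roughly normal.

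The reach is the tailoring of the individual session, the focal-point count and, through the focal points addressed, the Hypothesis 5 dosage measure. The Plaque Score and Gingival Index comparisons and the sample size are not directly affected, nor are the section 12.4 mediation models. The documents do not establish that any session was tailored wrongly, and this review does not say which key or cut-off is right.

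**What to change.** Reconcile section 3.2.3 with row 7a. State one response key for the perceived-risk scale, and say whether scores are reversed before the cut-off is applied. Then check the coding in the survey file and in the Focal Points Checklist against that statement.

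As a secondary check, confirm that the worries and fears scores are coded in the direction that rows 8a and 9a assume, because section 2.1 reports the pilot scores in the opposite numerical direction.

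The cost is a few lines of wording and one scoring check. No change to the design, the sample size or the primary analysis is needed.

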3.2.4 Moderator Variables

Demographic background information: Items include age, gender, building, length of time in building, length of time in U.S., marital status, race and ethnicity, current living arrangement, times moved in the past year, work status, religious engagement, income and income satisfaction, language use, telephone, transportation availability, home care and health insurance.

Health status: This will be measured by: (a) subjective health status, a single item, shown to be a valid measure of health status across ethnic groups, (b) an index assessing current health status based on self-report of diagnosis on 13 health problems common in older adults and used in earlier ICR studies, (c) a composite measure of physical health distress based on degree to which each problem prevents participation in normal daily activities.

Self-assessed Oral health status: measured with a five point Likert scale assessing subjective oral health status (Locker et al., 2000).

Activities of Daily Living: Activities of Daily Living (ADLs) a widely used measure of the functional status of an individual, It consists of 8 behaviors that indicate ability to take care of personal basic needs (Katz , 1983; Lawton & Brody, 1969)

CES-D. This is the 10-item short version of the CES-D Screening Instrument that measures depressive symptoms in community populations. The Spanish version of the 10-item CES-D has been validated for use with Puerto Rican older adults and has been used in several studies of older adults, including in public housing, in the study area (Radloff & Rae, 1979; Irwin, Artin, Oxman, 1999; Mahard, 1988; Robison, Gruman, Gaztambide, Blank, 2002; Robison, [name], Coman, Diefenbach, Radda, Gaztambide, et al., 2009; Diefenbach, Disch, Robison, Baez, Coman, 2009).

4 STUDY DESIGN

Overall Design: The study utilizes a modified fractional factorial design (MFFD) which compares the short term outcomes of the two intervention components: the tailored individual level brief intervention (AMI-PM) and the group level Campaign including embedded oral health skills development through practice-to-mastery (CA+PM). It also evaluates the effects of differential sequencing of these modes of delivery components in relation to short and longer term outcomes. Finally, it evaluates intervention mechanisms through mediational modeling of the cognitive and the behavioral components over time. The two intervention components are the individualized AMI-PM (Component A), and the group CA+PM (Component B). To evaluate sequencing we will randomize pairs of senior residences into two conditions: Condition 1 and Condition 2. Buildings in Condition 1 will initiate with Component A, followed by Component B. Buildings in Condition 2 will initiate with Component B, followed by Component A. This study design will allow us to compare the AMI-PM outcomes to CA+PM short term outcomes, and to determine which condition sequence (A+B or B+A) will produce the best clinical outcomes. Each of 3 cycles of Condition 1 (A+B) compared to Condition 2 (B+A) will take place over a 16-18 month period each in two matched buildings with an N of 60 per building (N per cycle of 120; total N for all three cycles approximately 360). We anticipate an attrition rate of approximately 25% and a final N of approximately 270 by the T3 measure, 135 in Condition 1 and 135 in Condition 2. Primary outcomes are improvements in gingival health and decreases in plaque scores.

A description of the study population: Participants will be recruited from low income senior housing in Central Connecticut. The population consists of independent living older adults many of whom have chronic health conditions. Residents also include adults less than 62 years of age residing in these buildings who are disabled. Residents must meet income guidelines and be over the age of 62 or be disabled children and adults between the ages of 18 and 61.

Methods for collecting data for assessment of study objectives: Data collection will consist of clinical assessment, and surveys evaluating changes in cognitive domains (See Section 16).

Clinical Assessments: Clinical assessments will be conducted to collect data on Plaque Scores and Gingival Index, described in Section 3.2.1. Trained and calibrated licensed hygienists will conduct the exams under the supervision of [name].

Referrals for Emergent Dental Needs: Emergent dental needs are not uncommon in this population; when found, they will be referred to the University of CT. School of Dental Medicine or to the nearest Community Health Center. Emergent dental needs include inability to eat due to tooth or mouth pain, visual swelling of the face or mouth, fever of >100.5 of probable dental origin, and oral lesion located in a high oral cancer risk area. Once participants have been treated for the emergent dental issue they will be offered the opportunity to continue with the study. Emergent needs will be ranked

12/1/2010

using the system employed by the NHANES dental teams: Level 1 - participant should see a dentist immediately; Level 2 - participant should see a dentist within the next 2 weeks; Level 3 - participant should see a dentist at his/her earliest convenience; Level 4 - participant should continue with his/her regular routine. The form is included in the appendix.

Training and Calibration of clinical assessments (Adapted from National Health and Nutrition Examination Survey Dental Examiners Procedures Manual

Training is divided into three phases as follows:

- 1. The instructional phase in which examination team members are familiarized with research examination procedures and criteria for research assessments.
- 2. The standardization phase in which they are trained to use standard procedures and apply standard criteria for the oral health assessments.
- 3. The calibration phase in which the degree of correlation within and among the examiners and the standard examiner is measured.

Instruction

The instructional phase of the training sequence was conducted by [name] DMD who served as the initial Clinical Director, and standardized examiner or gold standard, with experience as a researcher and examiner on the previous pilot study. [name] is the current Clinical Director and will conduct the instructional phase with any new dental hygienists who join the study. He has appropriate experience both as a researcher and clinician. Instructions are to be conducted in each type of oral health assessment (Gingival Index and Plaque Score). The trainer presents lectures on criteria for each of the oral health assessments to be used in the study. Lectures are accompanied by slides depicting a wide variety of possible observations and illustrating application of assessment criteria to those observations. The lecture-slide presentations on each assessment are followed by instructions on data recording for that assessment. Although the instructional phase consists primarily of lectures and slide presentations, some demonstrations of examination technique and equipment use are conducted. All phases of the training and calibration will be redone anytime there is a change in clinical examiners.

Standardization

The second phase of training is devoted to standardization. During this phase of training, the standard examiner reviews examination procedures and techniques and the criteria for each assessment, stressing the importance of consistency and uniformity among all examiners and the standard examiner in performing the examination and in applying the criteria to observations. Rationale for differences between a research examination and a diagnostic examination are discussed and professional ethics of

research examinations reviewed. A demonstration of the examination by the standard examiner and practice examinations by the examiners being trained is among the salient features of this phase. Standardization of all examiners will be achieved by examining 4 patients in the field replicating research subjects and conditions. Discussion will occur to aid standardization. The Clinical Director (standard examiner) will monitor and referee examinations and discussion of observations during these sessions.

Calibration

The reliability of the assessments is measured by determining the degree to which examiners can produce uniform and consistent results when performing independent replicate examinations without discussion. In this phase of training, the standard examiner and all examiners in training will each examine 4 patients who are similar in demographics to the study population. The standard examiner monitors the calibration session without discussing observations with any of the examiners.

Data from the calibration sessions are analyzed to measure correlation within and between each examiner and the standard examiner (e.g., Kappa and McNemar's Test). If correlations between each of the examiners and the standard examiner are not within acceptable ranges or some examiners are consistently higher or lower than the standard examiner (i.e., significant McNemar's test) additional training sessions will be scheduled.

Monitoring and Recalibration

Continual gathering of clean, reliable data in a consistent and uniform manner is one of the main objectives of the clinical control trial. Several quality control procedures will be carried out periodically to assure continuing quality of data gathered by the dental team throughout the duration of the study. As in the initial calibration, the standard examiner and all examiners will each examine 4 patients who are similar in demographics to the study population. Recalibration will occur prior to or at the beginning of each study cycle.

Expert Replication and Monitoring Field Operations

During the field operations, examiners and recorders should periodically review their training manuals to prevent deviation, or "drift" from the standards achieved during the training period. Particular attention should be devoted to uniform adherence to the criteria for making correct decisions about observations such as scoring of gingival indices and presence or absence of plaque. Strict compliance with infection control procedures is another important consideration for dental teams. In order to help the dental teams maintain their standards, the clinical director for the study will make periodic visits to field personnel to observe their performance and offer feedback on the results of their examinations. Field observations occur twice per assessor for each time

point. Observation and matched scoring for GI and Plaque Score occur once per assessor per time point. The standard examiner will choose one patient per each of the dental hygienists on whom the examination will be replicated. The replicated exam will be completed in paper format and compared to the one entered on the computer so as not to confound the data collection for the study. The purpose of these so called "expert replications" is to determine whether the examiners are maintaining the examination standards achieved during training, and to measure the degree of deviation, if any, from those standards. If correlation between the standard examiner and the field examiner is not within acceptable limits, retraining will be conducted.

Annual Retraining

The long duration of the study (5 years) requires the need for regularly scheduled retraining periods. In addition to the regularly scheduled recalibration sessions with the standard examiner, there will be an annual retraining session for each dental examiner, also conducted by the standard examiner.

Training and Calibration of Oral Hygiene Skills Assessment (Practice to Mastery and T0 – T3).

Training is divided into two phases as follows:

- The instructional phase in which research interventionists and dental hygienists are familiarized with oral hygiene instruction and oral hygiene practice to mastery skill assessment scale.
- 2. The standardization phase in which the interventionists and dental hygienists are trained to use standard procedures and apply standard criteria for the oral hygiene skills assessment (and oral hygiene instruction for the interventionists).

Instruction

The instructional phase of the training sequence was conducted by [name] DMD who served as the initial Clinical Director, and standardized examiner or gold standard, with experience as a researcher and examiner on the previous pilot study. [name] is the current Clinical Director and will conduct the instructional phase with any new intervention staff or dental hygienist who join the study. He has appropriate experience both as a researcher and clinician. Instructions will be given regarding the Oral Hygiene Skills Assessment Evaluation Form and each mastery level on the form. Demonstrations will be given using the tooth brushing models. Although the instructional phase consists primarily of lecture, slide presentations and video clips, some demonstrations of examination technique and models are conducted. All phases of the training and calibration will be redone anytime there is a change in field staff during the study.

Standardization

The second phase of training is devoted to standardization. During this phase of training, the standard examiner reviews oral hygiene instruction procedures and techniques used in oral hygiene education and the criteria for each assessment, stressing the importance of consistency and uniformity among all examiners and the standard examiner in performing the examination and in applying the criteria to observations. Rationale for differences between simple oral hygiene instruction and the practice to mastery evaluation are discussed and reviewed. A demonstration of the practice to mastery evaluation by the standard examiner and a rehearsal practice to mastery by the examiners being trained is among the salient features of this phase. Standardization of all examiners will be achieved by assessing the same 4 subjects in the field, replicating actual research conditions. Discussion will occur to aid standardization. The Clinical Director (standard examiner) will monitor and referee examinations and discussion of observations during these sessions.

Annual Retraining

The long duration of the study (5 years) requires the need for regularly scheduled retraining periods. There will be an annual retraining session for all study staff conducting the Oral Hygiene Skills Assessment, conducted by the Clinical Director.

In addition to the clinical and skills assessments, there will be annual retraining sessions for all study staff on the conduct of the survey and AMI process, conducted by the study PIs.

